**Figure 3. Treatment Schedule for Optional Open-Label Extension Period**

Chemo = chemotherapy; IP = investigational product.

### 3.1.5 Long-Term Follow-Up Period

After the Follow-Up Visit, all subjects will be contacted approximately every 6 months for up to 5 years by telephone during the Long-Term Follow-Up Period for documentation of vital status (if death occurred, record of date of death) and occurrence of secondary malignancies. If a secondary malignancy has occurred, the following information will be collected: date of onset and type of malignancy, as well as a written narrative from the clinical site summarizing the course of events leading up to diagnosis of the secondary malignancy.

### 3.2 Study Duration and End of Study

The study will consist of the following periods:

- Double-Blind Treatment Period and Observational Period of approximately 8 to 9 weeks,
- Optional OLE Period until the subject's current chemotherapy regimen changes or the subject completes chemotherapy, and
- Long-Term Follow-Up Period of up to 5 years.

The end of study ("study completion") is defined as the date of the last protocol-specified visit/assessment (including telephone contact) for the last subject in the Long-Term Follow-Up Period.

### 3.3 Data and Safety Monitoring Board

An independent Data and Safety Monitoring Board (DSMB) will assess the overall study status and safety of subjects. A DSMB charter will be developed to govern DSMB activities, which will pre-specify the rules for safety reporting and safety analyses to be presented to the DSMB. The DSMB will make formal recommendations about the conduct of the study and safety of study participants following each DSMB meeting.

### 3.4 Study Indication

The indication for this study is the treatment of CIT.

## 4 SELECTION AND WITHDRAWAL OF SUBJECTS

### 4.1 Inclusion Criteria for All Subjects

Subjects who meet all of the following criteria will be eligible to participate in the study:

1. Subject is  $\geq 18$  years of age at the time of informed consent;
2. Subject with a diagnosis with ovarian cancer, lung cancer (small cell or non-small cell), or bladder cancer, requiring systemic chemotherapy;
3. Subject is currently receiving a chemotherapy regimen given in a 21-day or 28-day cycle (other chemotherapy cycle lengths are not allowed), including 1 or more of the following agents or class of agents:
  - o Nucleoside analog, including gemcitabine and fluorouracil;
  - o Carboplatin or cisplatin;
  - o Anthracycline; or
  - o Alkylating agent;
4. Subject experienced severe thrombocytopenia, defined as 2 platelet counts  $< 50 \times 10^9/L$  measured at least 24 hours apart, during the qualifying chemotherapy cycle (Cycle X), of their current chemotherapy regimen. Platelet counts obtained per standard of care during Cycle X prior to consent may be used;
5. Subject is planned to receive the same chemotherapy regimen and the same dose(s) on Chemotherapy Day (Days 1-3) of Cycle X+1 as was given in the qualifying chemotherapy Cycle X;
6. Subject has an Eastern Cooperative Oncology Group (ECOG) performance status  $\leq 2$ ;
7. Subject has a life expectancy  $> 12$  weeks at Screening and is able to receive at least 2 additional cycles of the current chemotherapy regimen;
8. Females of childbearing potential must agree to use a highly effective method of contraception (eg, total abstinence; an intrauterine device; hormonal contraceptive given orally, by injection, or by implant; double barrier contraception (i.e., condom + diaphragm); or has a vasectomized partner with confirmed azoospermia) throughout the entire study period and for 30 days after investigational product (IP) discontinuation. If currently abstinent, the subject must agree to use an effective method as described above if she becomes sexually active during the study period or for 30 days after IP discontinuation.

Male subjects must be either surgically sterile or agree to use a double barrier contraception method (combination of male condom with either cap, diaphragm, or sponge with a spermicide) throughout the entire study period and for 30 days after IP discontinuation;

Note: All female subjects are considered to be of childbearing potential unless they are postmenopausal (at least 12 months consecutive amenorrhea and without another known or suspected cause) or have been sterilized surgically (ie, bilateral tubal ligation, hysterectomy, or bilateral oophorectomy) at least 1 month before dosing.
9. Subject is willing and able to comply with all aspects of the protocol; and

10. Subject must provide written informed consent.

#### 4.2 Exclusion Criteria for All Subjects

Subjects who meet any of the following criteria will be excluded from participation in the study:

1. Subject has experienced  $\geq$  Grade 2 CIT with a platelet count  $<75 \times 10^9/L$  (other than during the current chemotherapy treatment regimen) within 6 months of Screening;
2. Subject has a platelet count  $>175 \times 10^9/L$  at Visit 2 (-1 day);
3. Subject with any history of hematologic malignancies, including leukemia, myeloma, myeloproliferative disease, lymphoma, or myelodysplastic diseases;
4. Subject who received  $>2$  previous lines of chemotherapy (adjuvant/neoadjuvant therapy is considered a previous line; immunotherapy alone is not considered a previous line) or is receiving whole brain radiation during the study treatment period;
5. Subject with an alanine aminotransferase (ALT) or aspartate aminotransferase (AST)  $>5 \times$  upper limit of normal or total bilirubin  $\geq 3 \times$  upper limit of normal;
6. Subject has a known medical history of human immunodeficiency virus;
7. Subject has any known clinically significant acute or active bleeding (eg, gastrointestinal or central nervous system) within 7 days of Screening;
8. Subject has a known medical history of genetic prothrombotic syndromes (eg, Factor V Leiden, prothrombin G20210A, or ATIII deficiency);
9. Subject has a recent history (within 3 months of Screening) of significant cardiovascular disease (eg, congestive heart failure exacerbation, arrhythmia known to increase the risk of thromboembolic events [eg, atrial fibrillation], coronary artery stent placement, angioplasty, or coronary artery bypass graft);
10. Subject has a history of arterial or venous thrombosis within 3 months of Screening;
11. Subject has used vitamin K antagonists within 7 days of Screening (use of low molecular weight heparin, Xa inhibitors, or thrombin inhibitors is allowed);
12. Subject has a history of chronic platelet or bleeding disorders or thrombocytopenia due to an etiology other than CIT (eg, chronic liver disease or immune thrombocytopenia purpura);
13. Subject has used moderate or strong inducers of cytochrome P450 (CYP)2C or CYP3A4/5 (see [Appendix C](#)) within 7 days of Screening;
14. Subject has received a thrombopoietin receptor agonist (eg, eltrombopag or romiplostim) or recombinant human thrombopoietin for the treatment of CIT within 3 months of Screening;
15. Subject received a platelet transfusion within 72 hours of randomization;
16. Subject is unable to take oral medication;
17. Subject has any history of a concomitant medical condition that, in the opinion of the Investigator, would compromise the subject's ability to safely complete the study, such as unstable angina, renal failure requiring hemodialysis, or active infection requiring intravenous antibiotics;

18. Female subjects who are lactating or pregnant at Screening or the Baseline Visit (as documented by a positive serum or urine beta-human chorionic gonadotropin [ $\beta$ -hCG] test) ;
19. Subject has hypersensitivity to avatrombopag or any of its excipients; or
20. Subject is currently enrolled in another clinical study with any investigational drug or device within 30 days of Screening; however, participation in observational studies is permitted.

#### **4.3 Inclusion Criteria for Subjects to Continue Into the Optional Open-Label Extension Period**

Subjects who meet all of the following criteria will be eligible to continue into the optional OLE Period:

1. Subject is currently receiving the same chemotherapy agents as were given in the qualifying chemotherapy Cycle X;
2. Subject has an ECOG performance status  $\leq 2$ ;
3. Females of childbearing potential must agree to use a highly effective method of contraception as previously defined.

Male subjects must be either surgically sterile or agree to use a double barrier contraception method (combination of male condom with either cap, diaphragm, or sponge with a spermicide) throughout the entire study period and for 30 days after IP discontinuation;

Note: All female subjects are considered to be of childbearing potential unless they are postmenopausal (at least 12 months consecutive amenorrhea in the appropriate age group and without another known or suspected cause) or have been sterilized surgically (ie, bilateral tubal ligation, hysterectomy, or bilateral oophorectomy) at least 1 month before dosing.

4. Subject is willing and able to comply with all aspects of the protocol; and
5. Subject must provide consent to continue into the OLE Period.

#### **4.4 Exclusion Criteria for Subjects to Continue Into the Optional Open-Label Extension Period**

Subjects who meet any of the following criteria will be excluded from continuing into the optional OLE Period:

1. Subject has a platelet count  $>175 \times 10^9/L$  on the scheduled first day of dosing of avatrombopag prior to chemotherapy;
2. Subject with an ALT or AST  $>5 \times$  upper limit of normal or total bilirubin  $\geq 3 \times$  upper limit of normal;
3. Subject has any known clinically significant acute or active bleeding (eg, gastrointestinal or central nervous system) within 7 days of pre-chemotherapy IP treatment in OLE cycles;
4. Subject has used vitamin K antagonists within 7 days of pre-chemotherapy IP treatment in Cycle X + 3 (use of low molecular weight heparin, Xa inhibitors, or thrombin inhibitors is allowed);

5. Subject has used moderate or strong inducers of CYP2C or CYP3A4/5 (see [Appendix C](#)) within 7 days of pre-chemotherapy IP treatment in OLE cycles;
6. Subject is unable to take oral medication;
7. Female subjects who are lactating or pregnant (as documented by a positive urine or serum test).

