### **5.6 Prior and Concomitant Medications and/or Procedures**

#### **5.6.1 Excluded Medications and/or Procedures**

The following medications and/or procedures are excluded:

- Use of vitamin K antagonists;
- Use of thrombopoietin receptor agonists or recombinant human thrombopoietin;
- Use of moderate or strong inducers of CYP2C or CYP3A4/5 (see [Appendix C](#)); and
- Currently enrolled in another clinical study with any investigational drug or device within 30 days of Screening; however, participation in observational studies is permitted.

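### The open-label extension exclusions omit the recent-thrombosis bar applied at entry, so an on-study clot treated with LMWH, an Xa inhibitor or a thrombin inhibitor does not exclude by rule

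*Protocol*

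**What the plan says.** At entry, Protocol 4.2 criterion 10 excludes on this ground: "Subject has a history of arterial or venous thrombosis within 3 months of Screening". Criterion 7 does the same for bleeding: "Subject has any known clinically significant acute or active bleeding (eg, gastrointestinal or central nervous system) within 7 days of Screening". Criterion 17 adds a judgement-based bar that begins "Subject has any history of a concomitant medical condition that, in the opinion of the Investigator".

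For the OLE, Protocol 4.4 and the matching synopsis list open with "Subjects who meet any of the following criteria will be excluded from continuing into the optional OLE Period" and have seven exclusions: platelet count, liver tests, bleeding, vitamin K antagonists, CYP inducers, inability to take oral medication, and pregnancy or lactation. The bleeding bar is re-dated to "clinically significant acute or active bleeding (eg, gastrointestinal or central nervous system) within 7 days of pre-chemotherapy IP treatment in OLE cycles". The vitamin K antagonist item is dated to Cycle X+3 and adds that "use of low molecular weight heparin, Xa inhibitors, or thrombin inhibitors is allowed". The five inclusions in 4.3 cover same chemotherapy agents, ECOG status, contraception, compliance and, last, "Subject must provide consent to continue into the OLE Period".

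Section 6.5.1 applies the OLE criteria at Visit 13, and 3.1.4 requires them to be met again before each further OLE cycle. Section 5.6.1 separately lists "Use of vitamin K antagonists" among excluded medications. Section 9.1.2 names two adverse events of special interest (AESI): thromboembolic events and bleeding events.

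**The concern.** Of the two named AESI, bleeding has a dated bar at OLE entry and thromboembolism has none. A recent clot is a mandatory exclusion before the first double-blind dose, but the same recent history is left to judgement before an OLE course. I found no stated reason for the difference.

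The stake is patient safety in the extension. Section 1.5.3 mentions a portal vein thrombosis that the investigator considered possibly related to study drug (Study 305, chronic ITP, starting dose 20 mg) and one thrombotic event on 40 mg in Study 311 (chronic liver disease). Neither gives a rate for this population, but both show why the sponsor watches the event. The OLE gives 60 mg for 5 days before and 5 days after Chemotherapy Day, repeated each cycle until the regimen ends.

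**Working it through.** **1. List comparison.** Matching each OLE exclusion in 4.4 to its entry criterion in 4.2:

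- item 1 (platelets above 175 × 10^9/L) = criterion 2
- item 2 (liver tests) = criterion 5
- item 3 (bleeding) = criterion 7, re-dated to OLE cycles
- item 4 (vitamin K antagonists) = criterion 11, re-dated to Cycle X+3 only
- item 5 (CYP inducers) = criterion 13, re-dated to OLE cycles
- item 6 (oral medication) = criterion 16
- item 7 (pregnancy, lactation) = criterion 18

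So 7 of 20 entry exclusions are carried. All three carried items with a look-back window are re-dated. Criteria 10 and 17 are not carried. No OLE exclusion (0 of 7) and no OLE inclusion (0 of 5) refers to thrombosis.

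**2. Which clots pass.** Treatment with a vitamin K antagonist is caught by item 4 at Cycle X+3 and by 5.6.1 generally. Treatment with LMWH, an Xa inhibitor or a thrombin inhibitor is expressly allowed. A subject treated that way who meets the other items passes the Visit 13 check.

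**3. Would the clot still be recent at OLE start?** Set Cycle X+1 Day 1 as day 0, assume no delays, and take 3 months as 90 days.

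- First double-blind dose: day −5.
- First OLE dose, 5 days before Cycle X+3 Day 1: 2 × 21 − 5 = day 37 (21-day cycles) or 2 × 28 − 5 = day 51 (28-day cycles).
- Interval: 37 + 5 = 42 days, or 51 + 5 = 56 days.
- Cumulative delay needed to pass 90 days: 90 − 42 = 48 days, or 90 − 56 = 34 days.

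Unless delays exceed those figures, any clot from the first double-blind dose onward is still inside the 3-month window when the OLE begins.

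**4. Ceiling on exposure per affected subject.** Days from the clot to each OLE course start, counting starts within 90 days:

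| Clot on | 21-day cycles | 28-day cycles |
|---|---|---|
| first double-blind dose day | 42, 63, 84 (3 courses) | 56, 84 (2 courses) |
| day before OLE start | 1, 22, 43, 64, 85 (5 courses) | 1, 29, 57, 85 (4 courses) |

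A course is 5 + 5 = 10 doses, so the ceiling is 5 × 10 = 50 doses. There is no floor above zero: 3.1.3 foresees that Cycle X+2 may be the last cycle, entry criterion 7 asks only for the ability to receive at least 2 more cycles, and the investigator may withdraw the subject. The per-subject figure is therefore 0 to at most 50.

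**5. Number of subjects.** The documents give no thrombosis incidence in chemotherapy-induced thrombocytopenia, so no count can be derived.

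**The case against.** The best reply is that the OLE list is deliberately short (13 of 20 entry exclusions are not carried) and that subjects already on study are protected in other ways:

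- Section 4.5 allows discontinuation for an SAE or clinically significant adverse event, and separately for a condition exposing the subject to substantial risk.
- Section 4.5.1 says the investigator should contact the Medical Monitor if dosing is missed or interrupted.
- Section 9.1.2 sends every thromboembolic event to the sponsor within 24 hours, serious or not.
- Platelets must not exceed 175 × 10^9/L before each OLE course, and dosing is held above 400 × 10^9/L.
- The DSMB reviews safety (3.3).

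Much of this stands. A reader might infer that a subject with a clot faces no check before re-exposure; the documents do not support that. The safeguards narrow the gap without closing it. Withdrawal under 4.5 is permissive, the AESI rule is about reporting, the platelet limits do not look at thrombosis, and no per-subject DSMB bar is described. The Medical Monitor step is not triggered by a clot in Cycle X+2, when no study drug is given. The DSMB charter and Investigator's Brochure were not available and may add guidance.

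A second reply is that 3.1.4, in requiring subjects to keep meeting the inclusion and exclusion criteria, re-applies the entry list. The preceding sentence and 6.5.1 point to the OLE criteria. Even on the other reading, criterion 10 looks back from Screening and would miss a later clot.

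Third, the protocol offers no evidence on re-exposure after a clot. The background events come from other diseases, and 1.5.3 describes safety in Studies 310 and 311 as similar to placebo. That is right, and it limits how strongly the point can be put.

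**Conclusion.** The gap is real on the text: recent thrombosis is a rule-based exclusion at entry and is not one in the OLE. It calls for an inexpensive safety improvement. It is not an error in the randomised part, and the randomised efficacy and safety comparison is unaffected.

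The number affected is unknown, likely small and possibly zero. Per affected subject the exposure is 0 to at most 50 doses of 60 mg in courses started within 90 days of the clot. The ceiling assumes no chemotherapy delays, enough cycles remaining, no withdrawal, and 3 months read as 90 days.

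A reader might go further and infer that affected subjects would typically receive many courses, or that the plan shows harm from re-exposure. The documents support neither: they give no incidence, and many investigators may stop the drug after a clot. Confidence is high in the textual omission and lower in its practical effect.

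**What to change.** Add an eighth exclusion to 4.4 and to the synopsis list, for example: arterial or venous thrombosis in the 3 months before the start of the pre-chemotherapy course of any OLE cycle. Check it at Visit 13 and at each later equivalent (13.1, 13.2 and so on). It uses the sponsor's own entry window, and eligibility and adverse events are already assessed at that visit.

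The cost is slightly fewer OLE subjects and a protocol amendment, which under 12.3 goes through the same review and approval as the original, across approximately 75 sites. It could travel with another amendment.

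One limit remains: a check at Visit 13 does not catch a clot between the two halves of the same OLE course, where 4.5 and 4.5.1 would still have to serve. No matching cardiovascular exclusion is proposed, because the protocol cites no link to the drug and Amendment 1 argues against one in stable cardiac disease.

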#### **4.5 Withdrawal Criteria**

Participation of a subject in this clinical study may be discontinued for any of the following reasons:

- The subject withdraws consent or requests discontinuation from the study for any reason;
- Occurrence of any medical condition or circumstance that exposes the subject to substantial risk and/or does not allow the subject to adhere to the requirements of the protocol;
- Any serious adverse event (SAE), clinically significant adverse event, severe laboratory abnormality, intercurrent illness, or other medical condition which indicates to the Investigator that continued participation is not in the best interest of the subject;
- Pregnancy;
- Requirement of prohibited concomitant medication;
- Subject failure to comply with protocol requirements or study-related procedures; or
- Termination of the study by the Sponsor or the regulatory authority.

If a subject withdraws prematurely from the study due to the above criteria or any other reason, study staff should make every effort to complete the full panel of assessments scheduled for Visit 13 (for subjects not in the optional OLE Period) or Visit 17 (for subjects participating in the optional OLE Period). All subjects should continue into the Long-Term Follow-Up Period unless consent has been withdrawn. The reason for subject withdrawal must be documented in the electronic case report form (eCRF).

In the case of subjects lost to follow-up, attempts to contact the subject must be made and documented in the subject's medical records.

##### **4.5.1 Subjects with Investigational Product Interruption or Discontinuation**

Subjects who discontinue study drug will be followed for the entire study duration through the Long-term Follow-Up Period (unless the subject withdraws consent), and all procedures should be followed according to the protocol.

If a subject discontinues study drug due to an adverse event, the Investigator will attempt to follow the event until it has resolved or stabilized.

If a subject misses a dose of study drug, temporarily interrupts treatments (whether due to an adverse event or other reason), the Investigator should contact the Medical Monitor regarding how to handle treatment re-initiation or if permanent study drug discontinuation is required.

## 5 STUDY TREATMENTS

### 5.1 Treatment Groups

This is a Phase 3 randomized, double-blind, placebo-controlled study of the efficacy and safety of oral avatrombopag in subjects with CIT with active non-hematological cancers. The study consists of 4 periods: a Double-Blind Treatment Period, an Observational Period, an optional OLE Period, and a Long-Term Follow-Up Period.

Subjects in the Double-Blind Treatment Period will be randomized to one of 2 study arms: 60 mg avatrombopag (3 × 20 mg tablets) once daily or placebo (3 tablets).

Subjects in the Observational Period will not receive any IP.

Subjects in the optional OLE Period will receive 60 mg avatrombopag (3 × 20 mg tablets) once daily.

Subjects in the Long-Term Follow-Up Period will not receive any IP.

### 5.2 Rationale for Dosing

A PK/PD model was developed to simulate platelet response to avatrombopag administration in order to select a dose regimen for this study. Using data from healthy volunteers and subjects with CLD, the PK/PD model evaluated the relationship of avatrombopag concentrations to increases in platelet counts. As a part of this model, the effect of carboplatin dose on platelet count obtained from population PK/PD modeling of eltrombopag in subjects with advanced solid tumors with CIT was also incorporated. Simulations were performed assuming the baseline platelet count ranged between 25 and 150 × 10^9/L with a goal to increase the platelet count to levels >100 × 10^9/L for the duration of chemotherapy treatment to prevent platelet transfusion and to allow the subject to receive the same dose and schedule of chemotherapy as prescribed in Cycle X. Simulations suggested that 60 mg avatrombopag administered once daily for 5 days prior to chemotherapy and once daily for 5 days following chemotherapy was the most appropriate for maintaining platelet counts above this threshold while preventing platelet counts from elevating above the upper limit of normal.

To ensure the accuracy of the predictions, platelet response data will be reviewed by the DSMB as described in [Section 3.3](#), and if necessary, dosage adjustments may be made following these data reviews.

